### 11.13 – Tertiary Endpoint #13

**[Tertiary Endpoint #13 will only be assessed on the first 200 patients randomized, as generated for the Interim Analysis. A decision was made by the Executive Committee to not assay for BNP at trial completion for the remaining randomized patients.]**

Endpoint Description: The log of the proportional change from baseline in the area under the curve for the ratio of NT Pro BNP/BNP compared to baseline.

Response Variable Definition: The was collected at Baseline, Week 2, Week 4, Week 8, Week 12 and Week 24. The endpoint will be derived in a similar fashion to the primary endpoint (see 9.1).

Additional Covariates in Addition to Randomized Treatment: atrial fibrillation status at time of randomization, baseline value of log(BNP) and log(NT Pro BNP).

Handling of Dropouts and Missing Data: If missing biomarker data at Week 24, use last observation carried forward (LOCF) from previous post-Baseline time point with available data. No adjustment will be made for missing Baseline results.

Sensitivity Analysis: No sensitivity analyses will be performed.

Statistical Tests: A general linear model (PROC GLM in SAS) will be used to test the significance of differences in the area under the curve for the ratio of NT Pro BNP to BNP between the two treatment arms.

Interpretation of Results: A lower value for the NT Pro BNP/BNP ratio indicates an improvement in the LCZ696 arm versus Valsartan.

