4 OBJECTIVES

4.1 Primary Objectives

To evaluate the effects of LCZ696 compared to valsartan on the proportional change from baseline in the AUC for NT-proBNP levels at 2, 4, 8, 12, and 24 weeks.

Hypothesis: In patients with symptomatic, advanced heart failure due to left ventricular systolic dysfunction, treatment with LCZ696 for 24 weeks will improve NT-proBNP levels, which reflect hemodynamic and clinical status, compared to treatment with valsartan.

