5 BACKGROUND

Patients with advanced HFrEF have extremely high morbidity and mortality with 1 year outcomes of death and hospitalization of approximately 50%.^{1,3} Although ACEI/ARBs, beta-blockers and spironolactone are currently approved for use in patients with advanced heart failure (NYHA class IV), the overall morbidity and mortality in this class of patients remains unacceptably high. For the most advanced heart failure patients, the evidence base for medical treatment is limited with consensus guidelines recommending consideration for either cardiac transplant or ventricular assist device, or palliative care.³

Recently, a new class of therapeutic agent, a dual angiotensin receptor blocker (ARB) angiotensin receptor blocker neprilysin inhibitor (ARNIs) has been approved for use in patients with NYHA class II-IV heart failure. LCZ696 is an ARNI consisting of the neprilysin inhibitor sacubitril (AHU377) and the ARB valsartan. Neprilysin (NEP) is a membrane bound enzyme (peptidase) that can be “shed” and circulated in a biologically active form in the circulation. NEP catalyzes the degradation of a number of endogenous peptides, including natriuretic peptides, angiotensin II, bradykinin, substance and amyloid β peptide, which has been implicated in Alzheimer’s disease. In heart failure, NEP inhibition leads to increased circulating levels of these vasoactive peptides, thereby offsetting the deleterious effects of neurohormonal over activation, that contribute to peripheral vasoconstriction, sodium retention, and maladaptive left ventricular remodeling. In small clinical trials in patients with heart failure with a preserved ejection fraction or who had hypertension, LCZ696 had hemodynamic and neurohormonal effects that were greater than those of an ARB alone.

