6 PRELIMINARY STUDIES (STUDY RATIONALE)

The PARADIGM-HF trial showed that LCZ696 improved morbidity and mortality in patients with chronic HFrEF in comparison to enalapril.² In PARADIGM-HF, 8442 patients with class II, III, or IV heart failure and an ejection fraction of 40% or less were randomized to receive LCZ696 (at a dose of 200 mg twice daily) or enalapril (at a dose of 10 mg twice daily), in addition to evidence

based medical therapy for heart failure. The primary outcome variable for the trial was a composite of death from cardiovascular causes or hospitalization for heart failure. The trial was stopped early for benefit in the LCZ696 treatment arm. At the time of study closure, the primary outcome had occurred in 914 patients (21.8%) in the LCZ696 group and 1117 patients (26.5%) in the enalapril treatment arm (HR 0.80; 95% CI, 0.73 - 0.87; P < 0.001). Moreover, there was a significant overall mortality benefit for LCZ696 when compared to enalapril (HR 0.84; 95% CI, 0.76 - 93; P <0.001). Despite the striking clinical benefits for LCZ696 in the PARADIGM-HF trial, limited experience with advanced heart failure patients was gained from patients enrolled in the trial. In the PARADIGM-HF trial a total of 33 patients (0.8%) with class IV heart failure were randomized to the treatment arm with LCZ696. Moreover, a recent study by Vodovar in patients with acute decompensated heart failure suggests that high circulating levels of endogenous B-type natriuretic peptide (BNP) and proBNP are capable of inhibiting the enzymatic activity of circulating NEP,⁴ raising the possibility that the NEP inhibition may be less effective in patients with more advanced heart failure.

Because the information on the effects of sacubitril/valsartan in patients with NYHA class IV heart failure is limited, the updated 2016 ACC/AHA/HFSA guidelines for the treatment of heart failure do not endorse the use of sacubitril/valsartan in patients with NYHA class IV heart failure⁵

Accordingly, additional experience is needed on the use of, and outcomes with LCZ696 in patients unable to tolerate target doses of ACEI/ARB.

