16.2 Sample Size Justification and Randomization

Subjects will be randomized in a 1:1 allocation ratio using a permuted block design with stratification based on the clinical center and atrial fibrillation status. We plan to randomize 400 subjects with planned follow-up of 26 weeks. The primary efficacy endpoint is the proportional change from baseline in the AUC for NT-proBNP levels measured at 2, 4, 8, 12 and 24 weeks.

Based on recent Heart Failure Clinical Research Network (HFN) trials with similar follow-up requirements, we are anticipating a dropout / withdrawal of consent rate of approximately 5%. However, due to deaths and other sample collection issues we anticipate as many as 20-25% of subjects will not have NT-proBNP data at the week 24 assessment.

For the primary analysis, the AUC data will be log transformed and subjects missing the NT-proBNP data at the week 24 assessment will be assigned the last observation carried forward (LOCF). Based on a 2-sample t-test with type I error of 0.05 two-sided, the total sample size of 400 randomized subjects will provide 80% and 90% power to detect a differences of 19% and 21% for LCZ696 compared to valsartan. The PARAMOUNT phase II clinical trial observed a 23% greater reduction in NT-proBNP for LCZ696 compared to valsartan at 12 weeks post-randomization in patient population with HFpEF. ⁶ The HF Network investigators believe a 20% reduction in NT-proBNP would be considered a clinically significant improvement, and this level of change falls within a range considered clinically meaningful in a recent comparative effectiveness review published by AHRQ. ⁷

Sensitivity analyses will examine the influence of the imputation for the informatively missing data. For the complete case analysis, the total sample size of 400 subjects will provide approximately 80% and 95% power to detect reductions of 20% and 25% for LCZ696 compared to valsartan, respectively. These calculations were based on a two-sample t-test and assume that the standard deviation of the log-transformed 180-day AUC measure is 0.70. ⁸

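### SAP 11.13 reads a lower NT-proBNP/BNP ratio as improvement, but neprilysin inhibition can produce that contrast with no difference in NT-proBNP

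*SAP*

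**What the plan says.** SAP 11.13 compares the arms on the log AUC of the NT-proBNP/BNP ratio relative to baseline, using a general linear model adjusted for atrial fibrillation status, baseline log BNP and baseline log NT-proBNP. It covers the first 200 randomized patients and plans no sensitivity analysis. Its interpretation rule is: "A lower value for the NT Pro BNP/BNP ratio indicates an improvement in the LCZ696 arm versus Valsartan". The protocol lists the same endpoint (sections 4.3 and 13.3) without saying which direction is favourable.

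The protocol describes the pharmacology in two places. Section 5 says of neprilysin (NEP): "NEP catalyzes the degradation of a number of endogenous peptides, including natriuretic peptides". It adds that "NEP inhibition leads to increased circulating levels of these vasoactive peptides". Section 6 identifies BNP as a member of that class when it refers to "high circulating levels of endogenous B-type natriuretic peptide (BNP) and proBNP". The same section cautions about this population, "raising the possibility that the NEP inhibition may be less effective in patients with more advanced heart failure".

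Clinical meaning is attached to the numerator. Protocol 4.1 hypothesizes that LCZ696 "will improve NT-proBNP levels, which reflect hemodynamic and clinical status", and section 16.2 cites an earlier phase II trial that "observed a 23% greater reduction in NT-proBNP for LCZ696 compared to valsartan".

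**The concern.** A ratio can fall because its numerator falls or because its denominator rises. Here the protocol's own account gives the study drug a direct route to a higher denominator, and after randomization only one arm is assigned that drug. A between-arm difference in the ratio may then show only that neprilysin is being inhibited, yet the SAP has already labelled it an improvement.

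Nothing in the planned analysis separates the two explanations. Baseline covariates cannot remove a drug effect on BNP that differs between arms after randomization. The BNP AUC is not an endpoint, so no planned output shows which component moved. SAP section 4 calls any endpoint with a two-sided p-value of 0.05 or less significant and states no multiplicity control. At stake is the reporting: a nominally significant improvement on a biomarker ratio could stand beside a neutral NT-proBNP result.

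**Working it through.** The documents give no sample size, effect size or power for this endpoint, so there is no figure of the plan's own to reproduce. The calculation below illustrates how large the effect could be.

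**Inputs from the documents.** Visits at weeks 0, 2, 4, 8, 12 and 24; AUC by trapezoids on the ratio to baseline, then logged (SAP 9.1, applied by 11.13); first 200 patients at 1:1, taken as 100 per arm; two-sided alpha 0.05 (SAP 4). The only log-AUC SD given is 0.70, for NT-proBNP (Protocol 16.2).

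**Assumptions.** NT-proBNP is flat and identical in both arms. BNP is multiplied by a factor b whenever the patient is on LCZ696, with b from 1.05 to 1.50. The SD of the log ratio AUC is 0.3, 0.5 or 0.7. All 200 patients contribute.

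**Step 1: AUC.** If the ratio to baseline is 1 at week 0 and c from week 2 onwards, the area is (1 + c)/2 × 2 + 22c = 1 + 23c. With no change it is 24.

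**Step 2: which baseline.** Protocol 12.1 gives every patient open-label LCZ696 in the run-in and draws the core-laboratory baseline at Visit 2, at its end.
- Baseline fully on drug: LCZ696 stays at c = 1 and valsartan goes to c = b once LCZ696 stops. The between-arm ratio of AUCs is 24/(1 + 23b). At b = 1.30 this is 24/30.9 = 0.777. The mean ratio is 1.00 on LCZ696 and 30.9/24 = 1.29 on valsartan.
- Drug-free baseline: LCZ696 goes to c = 1/b and valsartan stays at 1. The between-arm ratio is (1 + 23/b)/24, which at b = 1.30 is 0.779.

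The size is nearly the same. Under the scheduled design, however, the contrast would come mainly from the ratio rising on valsartan, not from a fall on LCZ696.

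**Step 3: chance of p < 0.05 in favour of LCZ696.** This is Φ(|ln(between-arm ratio)| / (SD × √(2/100)) − 1.96). For b = 1.30 and SD 0.7: 0.253/0.0990 = 2.55, and Φ(2.55 − 1.96) = 0.72.

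| Assumed BNP rise | Between-arm ratio | SD 0.7 | SD 0.5 | SD 0.3 |
|---|---|---|---|---|
| 5% | 0.95 | 7% | 10% | 20% |
| 10% | 0.91 | 15% | 25% | 58% |
| 20% | 0.84 | 43% | 70% | 99% |
| 30% | 0.78 | 72% | 95% | about 100% |
| 50% | 0.68 | 98% | about 100% | about 100% |

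With no effect on either peptide, the chance in this direction would be 2.5%.

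**Step 4: does the ratio follow clinical status?** If both peptides worsen by 20% and the drug also raises BNP 1.3-fold, the ratio is 1.2/(1.2 × 1.3) = 0.77, which the rule reads as improvement. If both peptides fall by 20%, the ratio is 0.8/0.8 = 1.00 and the benefit is not seen.

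**The case against.** Five arguments deserve a hearing.

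1. The asymmetry between the two peptides is not stated. Section 5 speaks of natriuretic peptides as a class, and the protocol's abbreviation list expands NT-proBNP as a natriuretic peptide too. This stands as a stated assumption. Sections 4.1 and 16.2, which expect and cite lower NT-proBNP on LCZ696, make a drug-driven rise in the numerator unlikely but do not exclude it.

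2. A reader might infer that this endpoint is bound to favour LCZ696 whatever happens to patients. The documents do not support that. Section 6 raises the possibility of weaker inhibition in advanced heart failure, no size is given for the BNP rise, and at SD 0.7 a 10% rise gives a significant result in only about 15% of trials.

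3. A reader might also picture the ratio dropping on LCZ696. The post-run-in baseline makes a rise on valsartan the main source. This changes the description but hardly changes the between-arm size.

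4. The sentence says improvement without the word clinical, and may be template text giving a favourable direction, as in other SAP sections. That is fair: the SAP makes no explicit claim of clinical benefit here. But neither document says what else is improved, and a favourable direction still needs a basis.

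5. The primary endpoint is the NT-proBNP AUC itself, so the ratio would be read beside it, and SAP section 14 indicates that the primary endpoint was already assessed at the 200-patient interim. This limits the harm. It does not supply the BNP result needed to interpret the ratio.

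**Conclusion.** The interpretation rule in SAP 11.13 is not supported by the protocol's own mechanism. A lower between-arm ratio can reflect neprilysin inhibition alone, with no difference in NT-proBNP. The direction follows by arithmetic from two conditions: BNP is higher on LCZ696 because of the drug, and NT-proBNP is not raised by the same route. The first is the protocol's stated pharmacology, of uncertain strength in this population; the second is implied only.

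The probabilities illustrate the risk and do not predict the result. The BNP rise is assumed throughout, the ratio's SD is not given, and 0.70 is borrowed from the NT-proBNP AUC. Fewer than 100 evaluable patients per arm would lower them.

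The consequence is modest. This is the last of 13 tertiary endpoints, restricted to 200 patients, and neither the primary analysis nor the interim efficacy boundary depends on it. It is worth correcting because the stated rule is unsupported and the correction is cheap.

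**What to change.** In SAP 11.13, replace the interpretation sentence with: *A lower ratio is consistent with neprilysin inhibition (a pharmacodynamic marker) and will not by itself be interpreted as clinical improvement.* Add one descriptive table showing the NT-proBNP AUC and the BNP AUC separately by arm for the same first 200 patients, with a note that baseline was drawn at the end of the LCZ696 run-in.

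The cost is one sentence and one table. Both peptides are already assayed in these patients, so no new samples are needed, and the endpoint, test and sample size stay as they are.

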## 12. Exploratory Endpoint Descriptions

### 12.1 – Exploratory Endpoint #1

Endpoint Description: A four level modified clinical composite endpoint including 1) death, 2) LVAD or Heart Transplant (including listing status of 1A, 1B or 1-4), 3) multiple HF hospital admissions, and 4) single HF admission, using the pre-COVID-19 population.

Response Variable Definition: The unmatched approach to the win ratio of Pocock will be used. In general terms, each patient will be placed into one of the hierarchical groups based on the comparison of LCZ696 versus Valsartan patients. The hierarchy for the comparisons is as follows:

- (a) LCZ696 patient had death first
- (b) Valsartan patient had death first
- (c) LCZ696 patient had LVAD or HTP first
- (d) Valsartan patient had LVAD or HTP first
- (e) LCZ696 patient had multiple HF hospital admissions first
- (f) Valsartan patient had multiple HF hospital admissions first
- (g) LCZ696 patient had single HF hospital admission first
- (h) Valsartan patient had single HF hospital admission first
- (i) None of the above

Additional Covariates in Addition to Randomized Treatment: None

Handling of Dropouts and Missing Data: All patients are expected to have some data to address this endpoint. No further adjustments for incomplete or missing data will be made.

Sensitivity Analysis: Re-calculate the endpoint analysis using the original ITT population.

Statistical Tests: The win ratio approach of Pocock will be used to evaluate each endpoint. Calculation of the test statistics, p-values and confidence intervals is detailed in the Pocock manuscript (Pocock SJ, Ariti CA, Collier TJ, Wang D. The win ratio: A new approach to the analysis of composite endpoints in clinical trials based on clinical priorities. *Eur Heart J*.33:176-182).

Interpretation of Results: A win ratio of 1.0 is the null value. Estimates below 1.0 indicate a worse outcome and win ratios greater than 1.0 indicate a favorable effect for the LCZ696 arm.

### **13. Safety analysis**

#### **13.1 – Safety Endpoint #1**

Safety Endpoint #1: Comparison of serious adverse events at the level of MedDRA preferred term, using the pre-COVID-19 population.

Response Variable Definitions: The number of patients experiencing each unique serious adverse event (SAE) type based on MedDRA preferred term within body system.

Additional Covariates: None

Handling of Dropouts and Missing Data: No adjustments for missing data will be made.

Sensitivity Analysis: Re-calculate the endpoint analysis using the original ITT population.

Statistical Tests: Fisher's mid-p will be calculated for each serious adverse event based upon the unique MedDRA preferred term within a body system.

Interpretation of Results: Lower event rates indicate a better outcome for LCZ696 arm versus Valsartan.

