LCZ696 (sacubitril/valsartan): The use of LCZ696 compared to the guideline-indicated ACE inhibitor enalapril reduced mortality was shown in the PARADIGM trial to reduce the hazard ratio for cardiovascular death and mortality by 20%. The updated 2016 ACC/AHA/HFSA guidelines for the treatment of heart failure recommend the use of sacubitril/valsartan in patients with NYHA II-III heart failure (I, LOE B-R).⁵ Few enrollees in the PARADIGM trial had NYHA Class IV heart failure and enrollment required systolic blood pressure > 100 mmHg at the time of enrollment. The risks and benefits of LCZ696 among patients with advanced heart failure and lower enrollment blood pressure are not known, which is the rationale for this trial. The known risks of Entresto™ overlap with those of valsartan alone, with some initial considerations. In the PARADIGM trial, use of LCZ696 was associated with a greater incidence of angioedema than the comparator drug enalapril (0.5% vs. 0.2%). The risk of angioedema with LCZ696 compared to enalapril was relatively greater among Black patients (2.4% vs. 0.5%). Patients with a history of angioedema are contraindicated from taking this drug. Trial data indicate adverse reactions occurring ≥5% are hypotension, hyperkalemia, cough, dizziness, and renal failure. Symptomatic hypotension in PARAGON was more common among patients taking LCZ696 than enalapril (18% vs. 12%).

Use of drugs that act on the renin-angiotensin system during the second and third trimesters of pregnancy reduces fetal renal function and increases fetal and neonatal morbidity and death. Women of child-bearing potential must have a negative pregnancy test prior to initiating study drug. When pregnancy is detected, discontinue study drug as soon as possible. These adverse outcomes are usually associated with use of these drugs in the second and third trimesters of pregnancy. There is no information regarding the presence of sacubitril/valsartan in human milk, the effects on the breastfed infant, or the effects on milk production. Sexually active subjects must agree to use appropriate contraception as long as they are taking study drug. Medically acceptable contraceptives include:

- surgical sterilization (such as a tubal ligation or hysterectomy)
- approved hormonal contraceptives (such as birth control pills, patches, implants or injections)
- barrier methods (such as a condom or diaphragm) used with a spermicide, or
- Intrauterine device (IUD)

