15.4 Serious Adverse Events (SAE)

An adverse event or suspected adverse reaction is considered serious if the investigator or sponsor believes any of the following outcomes occurred:

- Death
- Life-threatening AE: Places the subject at immediate risk of death at the time of the event as it occurred. It does not include an AE that, had it occurred in a more severe form, might have caused death.
- Persistent or significant incapacity or substantial disruption of the ability to conduct normal life functions.
- Inpatient hospitalization or prolongation of hospitalization.
- Congenital anomaly or birth defect.
- Important medical events that may not result in death, be life threatening, or require hospitalization may be considered a serious adverse event when, based upon appropriate medical judgment, they may jeopardize the subject and may require medical or surgical intervention to prevent one of the outcomes listed in this definition above.

This determination is based on the opinion of either the investigator or sponsor (e.g., if either believes it is serious, it must be considered serious).

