15.9 Anticipated Disease Related Events and Events of Interest

The following are anticipated, disease-related events in patients with HF or anticipated events of interest in patients with heart failure taking valsartan or valsartan/sacubitril:

- **Arrhythmias:** This refers to both atrial and ventricular arrhythmias.
- **Sudden Cardiac Death:** This refers to witnessed cardiac arrests and sudden deaths without an otherwise apparent cause such as trauma or malignancy.
- **Acute coronary syndrome:** This refers to unstable angina, non ST segment elevation myocardial infarction (NSTEMI), and ST segment elevation myocardial (STEMI).
- **Unplanned hospitalization, ER visit or clinic visit for worsening HF:** This refers to treatment for acute heart failure such as receiving intravenous diuretics.
- **Cerebrovascular event:** This refers to cerebrovascular accidents (stroke) of any cause (hemorrhagic, ischemic, or embolic) and transient ischemic attack (TIA).
- **Venous thromboembolism:** This includes both deep venous thrombosis and pulmonary embolus.
- **Lightheadedness, Presyncope, or Syncope:** This includes dizziness, lightheadedness, or fainting from any cause.
- **Worsening renal function:** This refers to acute kidney injury, typically defined as a decrease in eGFR \geq 20% over 48 hours, or progressive loss of renal function over time.
- **LVAD implantation:** This refers to implantation of a temporary or durable LVAD.
- **Cardiac Transplantation**
- **Hyperkalemia \geq 5.5 mEq/L**
- **Acute renal failure with serum creatinine $>$ 2.5 mg/dL**
- **Angioedema**
- **Symptomatic hypotension**

Anticipated events will not be captured as AEs/SAEs during the study, but will be entered on the appropriate electronic case report form (eCRF) module (“Events of Interest” page).

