15.10 Recording and Reporting of Adverse Events

The site Investigator is responsible for monitoring the safety of subjects enrolled into the study at the study sites. For this study, non-serious AEs will not be collected on the safety reporting page of the eCRF, but should be documented in the source documents and followed according to local standard of care. Events significant enough to necessitate modification of study drug dosing will be captured on the appropriate eCRF module (“Study Drug Dosing” page).

All SAEs, except for those anticipated events listed above, occurring from signed informed consent through study visit 11 will be captured on the SAE eCRF. Subjects that have screen failed will be followed for SAEs until two weeks post last study drug dose. Unless exempted as described above, all SAEs, whether or not deemed drug-related or expected, must be reported by the investigator or qualified designee within 24 hours of first becoming aware of the event. For this study, the cause of death will be reported on either the SAE or Events of interest (EVNINT) eCRF, as well as the Death eCRF page. The investigator or qualified designee will enter the required information regarding the SAE into the appropriate module of the eCRF, which will automatically result in distribution of the information to DCRI Safety Surveillance. DCRI Safety Surveillance will share all SAE reports with Novartis Pharmaceuticals. If the eCRF system is temporarily unavailable, the event, including the investigator-determined causality to study drug should be reported via the back-up paper SAE form to DCRI Safety Surveillance. Upon return of the availability of the electronic data capture (EDC) system, the SAE information must be entered into the eCRF.

Any misuse or abuse of the study drug, other medication errors and uses outside of what is foreseen in the protocol (irrespective of whether a clinical event has occurred) must also be reported to DCRI.

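### The SAP's only safety comparison is of SAEs, so six anticipated event categories that the protocol keeps off the SAE form, angioedema among them, have no pre-specified by-arm summary of their own

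*SAP*

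**What the plan says.** SAP 13.1 is the only analysis under the safety heading: "Safety Endpoint #1: Comparison of serious adverse events at the level of MedDRA preferred term, using the pre-COVID-19 population". Each preferred term is tested with Fisher's mid-p, lower rates are read as favouring LCZ696, and the analysis is repeated in the full ITT population.

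Protocol 15.9 lists 14 anticipated disease-related events and events of interest, and then says: "Anticipated events will not be captured as AEs/SAEs during the study, but will be entered on the appropriate electronic case report form" (the Events of Interest page). Protocol 15.10 applies the same exemption to serious events: "All SAEs, except for those anticipated events listed above, occurring from signed informed consent through study visit 11 will be captured" on the SAE form. For other events, the same section states that "non-serious AEs will not be collected on the safety reporting page of the eCRF".

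The usual seriousness criteria are in Protocol 15.4 and include "Inpatient hospitalization or prolongation of hospitalization". Nothing in 15.9 or 15.10 brings an anticipated event back onto the SAE form once it meets one of them.

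Protocol 11.6 gives the background risks. It reports angioedema in 0.5% of patients on LCZ696 against 0.2% on enalapril in the earlier outcome trial. It also says: "Trial data indicate adverse reactions occurring ≥5% are hypotension, hyperkalemia, cough, dizziness, and renal failure". The lightheadedness/presyncope/syncope category in 15.9 takes in dizziness: "This includes dizziness, lightheadedness, or fainting from any cause".

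**The concern.** A stroke, an acute coronary syndrome or an episode of angioedema that leads to admission is serious by the protocol's definition, yet it goes to the Events of Interest page and not to the SAE form. SAP 13.1 reads only the SAE form. Followed as written, the plan produces a safety table from which these events are absent in both arms by design, and then interprets lower rates in that table as a better outcome for LCZ696.

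This matters more here than it would in a trial of a well-characterised population. Protocol 11.6 gives the unknown balance of risk and benefit in advanced heart failure with lower blood pressure as the reason for the trial. Angioedema and dizziness, both named there in connection with LCZ696, fall in categories for which the SAP sets out no count by arm.

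**Working it through.** No sample-size, power or alpha figure is involved. The check has two parts: a mapping of Protocol 15.9 to the SAP, and a small calculation of what a count could show.

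**Mapping.** Each of the 14 categories in Protocol 15.9 was compared with every endpoint in SAP sections 9 to 13.

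| Category in Protocol 15.9 | By-arm analysis in the SAP |
|---|---|
| Arrhythmias | none of its own |
| Acute coronary syndrome | none of its own |
| Cerebrovascular event | none of its own |
| Venous thromboembolism | none of its own |
| Lightheadedness, presyncope, syncope | none of its own |
| Angioedema | none of its own |
| Sudden cardiac death | only inside all-cause and cardiovascular death (11.1, 11.2) |
| Acute renal failure, creatinine > 2.5 mg/dL | only inside eGFR < 20 and eGFR change (10.4, 11.9) |
| Worsening renal function | 10.4, 11.9 |
| Hyperkalemia | 10.5 |
| Symptomatic hypotension | 10.3 (SBP ≤ 85 mmHg) |
| Worsening HF | 11.3 to 11.6, and IV diuretics in 11.11 |
| LVAD | 11.8, pooled with listing and transplant |
| Transplant | 11.8, pooled with listing and LVAD |

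Six categories have no analysis of their own. Two more are covered only within something broader, so a strict by-category reading gives 6 + 2 = 8. Six is the count that credits partial coverage.

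**Indirect routes for the six.** An event in one of them can still enter the analysis unlabelled:
- as hospital days in SAP 10.1, which counts all unplanned admissions;
- as a death in SAP 11.1 or 11.2;
- as a lower dose in SAP 10.2, where the SAP itself notes that reasons for dose reduction are poorly documented;
- as hypotension in SAP 10.3, if it was logged with SBP ≤ 85 mmHg.

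None of these shows how many patients per arm had the event.

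**Silence is not implied coverage.** SAP 10.3, 10.4 and 10.5 each define the response as a documented event of interest. The SAP therefore says so when it draws on that page; section 13 does not.

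**What a count could show.** Inputs: 335 patients in the pre-COVID-19 population and 365 randomised (SAP section 3); the 0.5% LCZ696 angioedema rate (Protocol 11.6). Assumption: equal arms.
- Per arm: 335/2 = 167.5; 365/2 = 182.5.
- Expected angioedema cases on LCZ696: 167.5 × 0.005 = 0.84; 182.5 × 0.005 = 0.91.
- Exact two-sided 95% upper limit after zero events in n patients: 1 − 0.025^(1/n). For n = 167 this is 2.2%; for n = 182 it is 2.0%.

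The expected counts are illustrative. The protocol does not give the source trial's follow-up time, exclusion criterion 2 and the run-in remove some susceptible patients, and no angioedema rate for valsartan is quoted. The zero-count limits assume complete follow-up, whereas 25 of the 335 patients have some visit data removed.

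**The case against.** The strongest reply is that other parts of the documents already provide for this. Protocol 18.1 says safety will be evaluated by comparing AEs and laboratory values between arms, and under the broad definition in 15.2 a stroke or angioedema is an AE. Protocol 16.3 sends the DSMB Chair a monthly summary of clinical and adverse events, and SAP section 14 describes quarterly safety review. SAP section 4 says categorical variables will be shown as counts and percentages, and Protocol 16.1 allows further exploratory analyses.

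This is partly right. A reader might infer that no by-arm safety review of these events exists at all, and the documents do not support that. But the DSMB provisions concern monitoring and list no categories. Protocol 18.1 speaks of AEs, while 15.9 says these events are not captured as AEs, so its reach is at best arguable. SAP section 4 is a formatting rule. None of them specifies a final Events of Interest table.

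The reply also stands on a second point. A reader might infer that the counts will never be seen. The documents show only that they are not pre-specified: nothing bars a descriptive table, and adding one later would not disturb error control.

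Three numerical readings are tempting and should be resisted:
- Treating six of 14 as a measured proportion. It depends on how partial coverage is credited. The strict reading gives eight, and counting the overlap of syncope with SAP 10.3 as coverage would give five.
- Turning the 5% threshold for dizziness into a guaranteed minimum number of cases. It comes from another trial with unstated follow-up, and patients here have first passed a tolerability run-in.
- Taking the angioedema rates that Protocol 11.6 quotes for Black patients as a ceiling for this trial. They are one scenario; the true rate in this population is unknown.

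**Conclusion.** The point holds as a gap in pre-specification. Protocol 15.9 and 15.10 together with SAP 13.1 produce an SAE table that leaves out serious arrhythmia, acute coronary syndrome, stroke, venous thromboembolism, syncope and angioedema in both arms, and no other SAP section summarises these categories by arm in their own right. Sudden cardiac death and acute renal failure are visible only within wider endpoints.

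It is not a loss of data, because the events are entered on the Events of Interest page. It changes no primary or secondary inference. It does limit what the planned analysis can say about safety, including a risk the protocol itself names. The conclusion rests on the text of these sections and not on any assumed event rate. It should be fixed.

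**What to change.** Add to SAP section 13 a descriptive table by arm giving the number and percentage of patients with at least one event in every Events of Interest category, with angioedema on its own line.
- **Window:** from randomisation to a stated cut-off. The documents use two candidates, Week 24 (the SAP tolerability endpoints) and study visit 11 (SAE capture); the table should say which applies.
- **Populations:** pre-COVID-19 and full ITT, the two that SAP 13.1 already uses.
- **Run-in:** a separate single-group count of the same categories during open-label LCZ696, since a table that starts at randomisation would miss them.
- **Testing:** none.

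The cost is SAP wording and a few extra tables. The protocol already provides for these events to be entered on the eCRF, so no new data collection is needed. The drawback is that counts in the rare categories will be too small to test and should be presented as descriptive only.
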